Amendment a	16-October 2023						
Original Protocol	01-September-2023						

Amendment: b

This amendment is considered to be nonsubstantial.

Overall Rationale for the Amendment:

This protocol has been amended to primarily address the FDA clinical non-hold comments regarding ophthalmological examinations, blood glucose monitoring, and treatment stopping criteria.

Minor editorial changes have also been made and are not presented in the summary of changes table.

Section # and Name	Description of Change	Brief Rationale				
Section 1.3.1: Part A: Single-Ascending Dose of LY3872386 in Healthy Participants	Added line item for bedside glucose monitoring to include time points on Day -1, Day 1, Day 2, and Day 7.	Updated to address FDA comments.				
	Added line item for hemoglobin A1c to include time points at screening, Day - 1, Day $29 \pm 1d$, Day $85 \pm 3d$, and ED.	Updated to address FDA comments and support additional treatment discontinuation and interruption criteria.				
	Added an ocular pressure, visual acuity, and cataract evaluation time point to Day $15 \pm 1d$ and $43 \pm 1d$. Provided additional to indicate that for follow-up Visit 802 and Visit 805, an ocular pressure assessment is required; additional visual acuity assessment may be conducted.	Updated to address FDA comments.				
Section 1.3.2: Part B: Multiple-Ascending Dose of LY3872386 in Patients with Atopic Dermatitis	Schedule: Added line item for hemoglobin A1c to include time points at screening, Day 1, Day 29 ± 1d, Day 85 ± 1d, Day 183 ± 3d, and ED.	Updated to address FDA comments and support additional treatment discontinuation and interruption criteria.				

Section # and Name	Description of Change	Brief Rationale					
	Added an ocular pressure, visual acuity, and cataract evaluation time point to Day $29 \pm 1d$, Day $57 \pm 1d$, and Day $88 \pm 1d$. Provided additional notes to state that for Visit 4, Visit 6, and follow-up Visit 801, an ocular pressure assessment is required; additional visual acuity and cataract assessment may be conducted.	Updated to address FDA comments.					
	Schedule: Added line item for hemoglobin A1c to include time points at screening, Day 1, Day $29 \pm 1d$, Day $85 \pm 1d$, Day $183 \pm 3d$, and ED.	Updated to address FDA comments and support additional treatment discontinuation and interruption criteria.					
	Added an ocular pressure, visual acuity, and cataract evaluation time point to Day $29 \pm 1d$, Day $57 \pm 1d$, and Day $88 \pm 1d$. Provided additional notes to state that for Visit 4, Visit 6, and follow-up Visit 801, an ocular pressure assessment is required; additional visual acuity and cataract assessments may be conducted.	Updated to address FDA comments.					
Section 1.3.3: Part C: Open- Label Multiple Dose of Prednisone in Healthy Participants	Prednisone mg and mg Dosing Schedule: Added line item for hemoglobin A1c to include a time point at screening.	Updated to address FDA comments and support additional screening criteria.					
	Prednisone mg Dosing Schedule: Added line item for hemoglobin A1c to include a time point at screening.	Updated to address FDA comments and support additional screening criteria.					
Section 5.2: Exclusion Criteria	Added Criterion #50 to exclude participants with a known history of diabetes.	Updated given that participants could have a higher risk to develop serious glucocorticoid related effects.					
	Added Criterion #51 to exclude participants with a fasting glucose level of ≥126 mg/dL and glycated hemoglobin ≥6.5% and/or taking antidiabetes medications at screening.						

Section # and Name	Description of Change	Brief Rationale						
	Added Criterion #52 to exclude participants with a known history of osteoporosis.							
Section 6.9: Prior and Concomitant Therapy	Updated the text to state that acetaminophen may be administered at the discretion of the investigator for the treatment of headache and so on.	Corrections to clarify the role of the investigator as opposed to the medical monitor.						
	Updated the text to state that antihistamine may be administered as a premedication for infusion at the discretion of the investigator.							
	Updated the text to state that if a need for concomitant medication arises, the inclusion or continuation of the participant may be at the discretion of the investigator after consultation with the sponsor.							
Section 7.1: Discontinuation of Study Intervention	Updated the section to include additional cardiovascular stopping criteria, ocular pressure interruption criteria, additional serious and opportunistic infections discontinuation and interruption criteria, abnormal laboratory parameters of special interest, including adrenal insufficiency criteria.	Updated to address FDA comments.						

1.1. Synopsis

Protocol Title:

A Phase 1, Multicenter, Randomized, Placebo-Controlled, Double-Blind, Single-Ascending Dose Study of LY3872386 in Healthy Participants, a Multiple-Ascending Dose Study of LY3872386 in Patients with Atopic Dermatitis, and an Open-Label Multiple-Dose Evaluation of the Safety and Tolerability of Prednisone in Healthy Participants.

Brief Title:

A Single-Ascending Dose Study of LY3872386 in Healthy Participants, a Multiple-Ascending Dose Study of LY3872386 in Patients with Atopic Dermatitis, and an Open-Label Multiple-Dose Evaluation of Prednisone in Healthy Participants.

Regulatory Agency Identifier Number(s): IND: 166698

Rationale:

LY3872386 is an ADC consisting of an anti-IL-4R antagonist mAb covalently conjugated via a linker to a small molecule GC (payload or LY3558533, also known as LSN3558533). Study J4L-MC-KMAA (KMAA) is a first-in-human study to characterize the safety, tolerability, and pharmacokinetics (PK) of single doses of LY3872386 in healthy participants and repeat doses in patients with atopic dermatitis (AD). Additionally, this study will assess the safety, tolerability, and PK of multiple dose levels of prednisone in healthy participants who will receive prednisone by mouth (PO) once daily (QD). The data generated in this study will guide the design of subsequent clinical trials.

Objectives and Endpoints:

Objectives	Endpoints
Primary	
• To characterize the safety of LY3872386 after single dose administration in healthy participants and after repeat dose administration in patients with atopic dermatitis.	Number and incidence of AEs, TEAEs, and SAEs
• To assess the safety of prednisone in healthy participants receiving multiple PO QD doses in various dosing groups.	Number and incidence of AEs, TEAEs, and SAEs
Secondary	
To characterize the PK of LY3872386, total antibody, and LY3558533 (free payload) following single dose administration in healthy participants and after repeat	C _{max} and AUC of LY3872386, total antibody, and LY3558533 (free payload)
 dosing in patients with atopic dermatitis. To characterize the PK of prednisone in healthy participants 	C _{max} and AUC of prednisone and prednisolone
receiving multiple PO QD doses in various dosing groups.	

Abbreviations: AE = adverse event; AUC = area under the concentration versus time curve; C_{max} = maximum observed drug concentration; PK = pharmacokinetics; PO = oral administration; QD = once daily; SAE = serious adverse event; TEAE = treatment-emergent adverse event

Statistical Considerations:

Treatment-emergent adverse events (TEAEs), serious adverse events (SAEs), and adverse events (AEs) for each IP will be listed and, if the frequency of events allows, descriptive statistics will summarize the safety data per race and ethnicity. Symptoms, their incidence, severity, and association with investigational product, as perceived by the investigator, will be reported separately for each treatment and IP. All TEAEs will be summarized across each part of the study by system organ class and by decreasing frequency according to the Medical Dictionary for Regulatory Activities.

Overall Design:

Study KMAA is a first-in-human trial designed to characterize the safety and tolerability of LY3872386 as well as the PK of LY3872386, total antibody, and LY3558533 (free payload) in healthy participants and in patients with AD. Additionally, this study will assess the safety, tolerability, PK, and pharmacodynamics (PD) of various dose levels of prednisone in healthy participants. The study will enroll participants of any ethnicity.

The study will be conducted following 3 parts:

- Part A (single-ascending dose [SAD] of LY3872386) will characterize the safety, tolerability, PK, and PD after single intravenous (IV) and subcutaneous (SC) dose administration of LY3872386 in healthy participants.
- Part B (multiple-ascending dose [MAD] of LY3872386) will characterize the safety, tolerability, PK, and PD after multiple SC and/or IV dose administrations of LY3872386 in patients with AD.
- Part C CCI will assess the safety, tolerability, PK, and PD after repeat PO administration of prednisone in healthy participants.

Brief Summary:

Part A is a randomized, placebo-controlled, sponsor-unblinded, investigator- and participant-blinded SAD study in healthy participants for LY3872386. Part B is a randomized, placebo-controlled, sponsor-unblinded, investigator- and participant-blinded, repeat, MAD study in patients with AD for LY3872386. Part C is an open-label study in healthy participants who will receive multiple doses PO QD of prednisone.

Study details include:

Treatment Arms, Duration, and Visit Frequency:

Part A: SAD of LY3872386 in Healthy Participants

Eligible participants will be admitted to the clinical research unit (CRU) on Day -1. Participants will receive a single-dose administration on Day 1 and will remain inpatient for approximately 7 days followed by visits at regular intervals.

A total of IV dose cohorts (CC) mg and mg) and SC dose cohorts mg and mg) are planned. Cohort 4 will include Japanese participants and Cohorts 6, 7,

and 8 will include Japanese and Chinese participants. The study intervention will be administered as a single dose on Day 1, followed by a 12-week follow-up period (Section 1.2).

Within each dose cohort, treatment-matched placebo will be given using the same time, frequency, and route as LY3872386, as applicable.

Part B: MAD of LY3872386 in Patients with Atopic Dermatitis

Eligible patients with AD will receive multiple doses of LY3872386 within a 12-week treatment period, with administration at an interval of at most CCI and/or at least CCI. Each dosing and discharge are at the discretion of the investigator, with visits in between the doses and at regular intervals following the last dose of the study drug.

At least 2 IV and/or SC dose cohorts (CC) mg and CC mg) are planned. The study intervention is planned to be administered on Day 1, followed by dose administration and/or CC for up to 12 weeks in patients with AD. The route and frequency of administration are planned to be the same for all participants within a cohort. The dose, route, and frequency of administration will be confirmed based on emerging data from the safety and PK data of previous SAD and MAD cohorts. Participants will be followed up for 14 weeks after the last dose (Section 1.2).

Within each dose cohort, treatment-matched placebo will be given using the same time, frequency, and route as LY3872386, as applicable.

Part C: Open-label Multiple Doses of Prednisone in Healthy Participants

Eligible participants will be admitted to the CRU on Day -2. Participants will receive multiple doses of either CCI may of prednisone during 1 treatment period.

One cohort with 3 dose levels (CC) mg) is planned. A prednisone tablet is planned to be administered to healthy participants and taken PO on Day 1, followed by QD PO dose administration. The mg and mg prednisone groups' safety and PD data will be reviewed to determine if the 1 mg prednisone group will be conducted and/or if the dose may be altered. Participants in the mg and the mg (if conducted) groups will receive prednisone for a total of 30 days. Participants in the mg group will receive prednisone for a total of 7 days. Participants in all groups will be followed up for 2 weeks after the last dose of prednisone (Section 1.2). The mg and mg prednisone dose groups may occur in parallel with each other as well as in parallel to Part A SAD or Part B MAD.

- mg or mg dose levels
 - o PO QD dosing in healthy participants for a total of 30 days, then a 2-week follow-up period after each dose level
 - o Inpatient for approximately 30 days with follow-up period following the last dose of each dose level.
- mg dose level
 - o PO QD dosing in healthy participants for a total of 7 days, then a 2-week follow-up period
 - o Inpatient for approximately 7 days with follow-up period following the last dose.

Number of Participants:

participants (healthy participants and patients with AD) may be enrolled to ensure that CCl evaluable participants (CCl healthy participants and up to patients with AD) complete the study. Participants will include:

- healthy participants enrolled in Part A (SAD cohorts) on LY3872386
 - evaluable healthy participants
 - o replacements
- Up to patients with AD enrolled in Part B (MAD cohorts) on LY3872386
 - o Up to evaluable patients with AD)
 - o replacements
 - o Japanese patients are not intended to exceed more than approximately of the total evaluable patients with AD (for example up to approximately patients with AD)
- healthy participants enrolled in Part C (multiple dose cohort) on prednisone
 - o evaluable participants
 - o replacements

Ethical Considerations of Benefit/Risk: Not applicable

Data Monitoring Committee: No

1.3. Schedule of Activities (SoA)

1.3.1. Part A: Single-Ascending Dose of LY3872386 in Healthy Participants

1.3.1. Part A	ı. omgr	-ASC	enaing D	Part A: S									Particip	ants					
Procedures / Assessments	Screen	ning	Treatment Period									E D	Comments						
Visit Number	V1		l	•	V2					V 801	V 802	V 803	V 804	V 805	V 806	V 807	V 808		
Study Day	C	C																	
Informed consent	X																		
Review/confirm I/E criteria	X	X																	
Admission to CRU		X																	CUI
Randomization			P																
Discharge from CRU									X										
Outpatient visit										X	X	X	X	X	X	X	X	X	
Clinical Assessments	3																		
Complete medical history	X																		
Review AEs	X	X	P	X	X	X	X	X	X	X	X	X	X	X	X	X	X	X	
Concomitant medications	X	X	P	X	X	X	X	X	X	X	X	X	X	X	X	X	X	X	
Substance use (alcohol and tobacco use)	X	X											X				X	X	CCI
Physical examination	X	X											X		X		X	X	

]	Part A: S	ingle	-Asce	ending	g Dose	of LY	387238	6 in H	ealthy I	Particip	ants					
Procedures / Assessments	Screei	ning	Treatment Period							Follow-up									Comments
Visit Number	V1			V2					V 801	V 802	V 803	V 804	V 805	V 806	V 807	V 808			
Study Day	C	C																	
Weight	X	X															X	X	
Height	X																		
Vital signs	X	X	X	X	X	X	X	X	X	X	X	X	X	X	X	X	X	X	
ECGs	X		P	X	X		X		X		X		X		X		X	X	
Chest x-ray, if indicated (posterior-anterior view)	X																		
QuantiFERON®-TB Gold test or TST	X																		
IP administration			X																
Laboratory Assessm	ents	1								 									
Serologies, syphilis, and FSH	X																		
Thyroid-stimulating hormone, including T3/T4 tests		X															X	X	OOI
Serum immunoglobulins	X		P						X		X		X		X		X	X	

			P	art A: Si	ngle-	Asce	nding	g Dose	of LY	387238	6 in He	ealthy I	Particip	ants					
Procedures / Assessments	Screen	ning		Treat	men	t Peri	iod						Follo	ow-up				E D	Comments
Visit Number	V1			V	2					V 801	V 802	V 803	V 804	V 805	V 806	V 807	V 808		
Study Day	C																		
CCI			<1-, 15-, 120-, and 240-min post injection	24 hr	X	X			X		X		X						CCI
Urinary drug screen (including ethanol breath test)	X	X																	
Pregnancy test	X	X															X	X	
Clinical chemistry	X	X	P	X	X		X		X	X	X	X	X	X	X	X	X	X	
Bedside glucose monitoring		X	P and 12 hr	24 hr and 36 hr					X										
Fasting lipid panel			P										X					X	
Hematology	X	X		X	X		X		X		X	X	X	X	X	X	X	X	
Hemoglobin A1c	X	X											X				X	X	
Urinalysis	X	X		X	X		X		X		X		X	X			X	X	

			P	art A: S	ingle	-Asce	ending	g Dose	of LY	387238	6 in He	ealthy I	Particip	ants					
Procedures / Assessments	Screen	ning		Trea	tmen	t Per	iod						Follo	ow-up				E D	Comments
Visit Number	V1			V	72					V 801	V 802	V 803	V 804	V 805	V 806	V 807	V 808		
Study Day	C	C																	
Pharmacogenetics			Р																CCI
Immunogenicity			P								X		X		X		X	X	
LY3872386, total antibody, and LY3558533 (free payload) concentration (PK)			P, EOI, 3 hr, 6 hr, and 12 hr	X	X	X	X	X	X	X	X	X	X	X	X	X	X	X	
			Р	X		X			X		X	X	X	X	X	X	X	X	
OO!			Р	X		X			X		X	X	Х	X	X	Х	X	X	
			P	X					X		X						X	X	
			P	X		X			X		X		X		X		X	X	
			P			X			X		X		X		X		X	X	
		X							Х		X	X	X		X		X	X	

			P	art A: Si	ingle-	-Asce	ending	Dose	of LY	387238	66 in He	ealthy I	Particip	ants					
Procedures / Assessments	Screen	iing		Trea	tmen	t Per	iod						Follo	ow-up				E D	Comments
Visit Number	V1			V	72					V 801	V 802	V 803	V 804	V 805	V 806	V 807	V 808		
Study Day	C																		
Cortisol		X	P and 12 hr	X	X	X	X	X			X			X					CCI
CCI			X	X	X	X	X	X											
CCI		X							X		X		X		X		X	X	

			P	art A: S	ingle-	-Asce	nding	Dose	of LY	387238	6 in He	althy F	articip	ants					
Procedures / Assessments	Screen	ning		Trea	tmen	t Peri	od						Follo	w-up				E D	Comments
Visit Number	V1			V	V 2					V 801	V 802	V 803	V 804	V 805	V 806	V 807	V 808		
Study Day	C																		
Ocular pressure, visual acuity, and cataract evaluation	Х										X			X			X	X	CCI

Abbreviations: AE = adverse event; CRU = clinical research unit; CCl CXR = chest x-ray; d = day(s); ECG = electrocardiogram; ED = early discontinuation; EOI = end of IV infusion or subcutaneous dose administration; FSH = follicle-stimulating hormone; hr = hours; I/E = inclusion/exclusion; IP = investigational product; min = minutes; P = predose before IP administration; CCl PK = pharmacokinetic; SAD = single-ascending dose; TB = tuberculosis; TST = tuberculin skin test; V = visit.

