2.3. Benefit/Risk Assessment

The toxicology data for LY3872386 demonstrate an acceptable nonclinical safety profile and margin of safety to support the transition from preclinical status to a clinical single-dose study in healthy participants and a multiple-dose study in patients with AD.

The nonclinical safety profile of LY3872386 is generally consistent with its intended pharmacology. Primary safety concerns predicted from studies with the ADC and the payload are bacterial and other infections, secondary to decreases in lymphoid tissue lymphocytes and circulating blood lymphocytes. Other potential risks identified for LY3872386 in toxicology studies and consistent with GC pharmacology are

- atrophy of skin hair follicles, especially near SC injection sites, potentially leading to thinning hair or hair loss
- suppression of the HPA axis
- increased serum triglycerides, and
- increased serum glucose.

The safety and efficacy associated with modulation of the IL-4/IL-13/IL-4R axis have been evaluated with approved drugs such as dupilumab and tralokinumab, and the safety and efficacy of GCs as a class are well-established. The key safety concerns and PD effects of LY3872386, including infection, conjunctivitis, hypersensitivity reactions, local injection site reactions, and systemic GC exposure from LY3558533 (free payload), will be closely monitored during the clinical study.

As with other immunomodulatory therapies, LY3872386 and prednisone may increase the risk of developing infections, increase the risk of an infection becoming more serious, and/or change the effectiveness of vaccines administered. LY3872386 may also increase the risk of opportunistic infections and the reactivation of latent infections. Participants will therefore be screened for hepatitis B, hepatitis C, HIV, and TB. In addition, all participants should be monitored for symptoms and signs of infection after administration of LY3872386 or prednisone.

Infusion reactions and hypersensitivity reactions are potential risks for all biologics. These risks will be carefully monitored during the dosing period in Parts A and B (the LY3872386 portions of the study), with close observation after infusion and stopping rules that prevent re-challenge of patients/participants with significant hypersensitivity reactions.

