4.2. Scientific Rationale for Study Design

Study KMAA is the first-in-human dose study that will characterize the safety, tolerability, and PK of single doses of LY3872386 in healthy participants, multiple doses of LY3872386 in patients with AD, and multiple dose levels of prednisone in healthy participants. Participants receiving prednisone PO QD will not be blinded with a placebo. Blinding of subjects to prednisone was not deemed necessary as only objective safety and PD biomarker results following prednisone or LY3872386 administration will be compared. A lack of blinding would not be expected to affect these results. The data generated in this study will guide the design of the subsequent clinical trials.

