10.2. Appendix 2: Clinical Laboratory Tests

The tests detailed in the table below will be performed by the central laboratory except for the following which will be performed at the local laboratory:

- Safety testing for immediate participant assessment
- Screening assessments in Part A and Part C.

In circumstances where the sponsor approves local laboratory testing in lieu of central laboratory testing (in the table below), the local laboratory must be qualified in accordance with applicable local regulations.

Protocol-specific requirements for inclusion or exclusion of participants are detailed in Section 5 of the protocol.

Additional tests may be performed at any time during the study as determined necessary by the investigator to address any immediate patient safety concerns.

Investigators must document their review of the laboratory safety results.

Laboratory results that could unblind the study will not be reported to investigative sites or other blinded personnel.

Safety Laboratory Tests

TH	GILL LGI
Hematologya	Clinical Chemistrya
Hematocrit	Sodium
Hemoglobin	Potassium
Erythrocyte count (RBC)	Bicarbonate
Mean cell volume	Chloride
Mean cell hemoglobin	Calcium (total)
Mean cell hemoglobin concentration	Phosphorus/Phosphate
Leukocytes (white blood cells [WBCs])	Glucose (fasting)
Platelets	Blood urea nitrogen (BUN)
Differential WBC (absolute counts) of	Creatinine
Neutrophils	Total protein
Lymphocytes	Albumin
Monocytes	Total bilirubin
Eosinophils	Alkaline phosphatase (ALP)
Basophils	Aspartate aminotransferase (AST)
B Cells	Alanine aminotransferase (ALT)
T Cells	Gamma-glutamyl transferase (GGT)
NK cells	Insuline
Hemoglobin A1c	Bedside Glucose Monitoring (fasting)f
Urinalysis ^a	Serum Immunoglobulinsa
Specific gravity	IgA
рН	IgM
Protein	IgE
Glucose	IgG
Ketones	IgD
Bilirubin	192
Urobilinogen	Fasting Lipid Panel ^a
Leukocytes	Total cholesterol
Blood	Triglycerides
Nitrite	Low-density lipoprotein (LDL)
	High-density lipoprotein (HDL)
Microscopic examination of sedimentb	
	LDL/HDL ratio
H. D. C.	T W D C W all
Urine Drug Screen ^c	Hepatitis B surface antigeng,h
Amphetamine	Hepatitis B core antibodyg,h
Barbiturates	Hepatitis B surface antibodyg,h
Benzodiazepines	Hepatitis B DNAh
Cocaine	Hepatitis C antibodyg,h
Cannabis	riepatitis C antibody
Methylenedioxymethamphetamine (MDMA)	
Opiates	
Oxycodone	
Phencyclidine	
Tricyclic antidepressants	
Cotinine (nicotine)	
	gh
Ethanol breath testing ^c	$HIV^{g,h}$
QuantiFERON®-TB Gold test or TST	Pregnancy test ⁱ

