10.2.1.1. Part A: SAD of LY3872386 in Healthy Participants

Purpose	Blood Volume per Sample (mL)	Number of Blood Samples	Total Volume (mL)
Screening tests ^a	45	1	45
Clinical chemistry ^a , including insulin and fasting lipid panel	4.5	8	36
Clinical chemistry ^a , including insulin, fasting lipid panel, serum immunoglobulins	8	6	48
Hematology, including TBNK	4	12	48
TSH, T3/T4	3.5	2	7
Pharmacokinetics ^b	6	19	114
CCI			
Cortisol	2	9	18
Cosyntropin stim – Cortisol (pre stim and 30-, 60-min post stim)	2	6 x 3 time points	36
Ex vivo stimulation	1	5	5
Cytokines (IL-4, IL-5, sCD163)	2.5	8	20
CCI			
Blood discard for cannula patency	1	5	5
Blood samples for receptor occupancy flow cytometry	2	11	22
Immunogenicity ^b	5	5	25
Pharmacogenetics	3	1	3
Total			501.5
Total for clinical purposes (rounded up to	nearest 10 mL)	1	510

Abbreviations: CC IIL = interleukin; IV = intravenous; CC PK = pharmacokinetic; SC = subcutaneous; TBNK = T, B, and Natural Killer; TSH = thyroid-stimulating hormone.

Additional samples may be drawn if needed for safety purposes.

b Additional 3 samples may be drawn if required.

^c If more than 1 laboratory blood draw is scheduled at the same time, these blood draws should be prioritized in the following order: (1) safety laboratory tests, (2) PK samples, (3) receptor occupancy samples, and (4) exploratory samples.

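### Triglycerides are a named risk, but Part A schedules one lipid panel after the dose and Part B schedule 1.3.2.2 only predose panels, while the blood-volume tables put lipids in every post-screening chemistry draw

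*Protocol*

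**What the plan says.** The list of potential risks in Protocol Section 2.3 contains the entry "increased serum triglycerides, and", followed by raised serum glucose. In Section 10.2 (Appendix 2), "Triglycerides" appears under the fasting lipid panel and not under clinical chemistry, so triglycerides are measured only where that panel is run.

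The "Fasting lipid panel" rows of the schedules of activities read:

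- **Part A (1.3.1):** Day 1 predose, V804, early discontinuation (ED).
- **Part B (1.3.2.1), dosing at every visit V2 to V8:** predose at V2, V4 and V6; V801; ED.
- **Part B (1.3.2.2), dosing at V2, V4, V6 and V8:** predose at those four visits; ED.

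The blood-volume tables say something different. In Section 10.2.1.1 one chemistry line is described as "including insulin and fasting lipid panel" (8 samples) and the other as "including insulin, fasting lipid panel, serum immunoglobulins" (6 samples). The two Part B tables use equivalent labels. Section 8.2.5 makes the schedule of activities the authority for which laboratory tests are run.

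**The concern.** The toxicology findings point to a lipid effect, yet lipids are measured far less often than the rest of the chemistry panel. Glucose is the neighbouring entry in the same risk list. It is measured at every Part A chemistry draw and also has bedside monitoring up to the end of the inpatient stay. Triglycerides get one scheduled value after the single dose, four weeks later.

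The stake is detection. A rise that came and went before Day 29 in Part A, or that appeared between doses or after the last dose under schedule 1.3.2.2, would have no scheduled sample to show it. In addition, a laboratory reading Section 10.2.1 and one reading the schedule would run different numbers of panels, and the choice could vary by site.

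**Working it through.** **Step 1. Reproduce the table counts.** Count chemistry marks in each schedule, leaving out screening (which has its own line in the tables) and ED.

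- Part A: Day -1, Day 1 predose, four inpatient days, V801 to V808. That is 1 + 1 + 4 + 8 = 14. Table: 8 + 6 = 14.
- Schedule 1.3.2.1: V2 to V8 and V801 to V804. That is 7 + 4 = 11. Table: 7 + 4 = 11.
- Schedule 1.3.2.2: V2, V3, V4, V6, V7, V8, V803, V804, V805. That is 6 + 3 = 9. Table: 5 + 4 = 9.

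All three agree exactly, so the tables attach the lipid panel to every post-screening chemistry draw in Parts A and B.

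**Step 2. Count the lipid panels actually scheduled (ED excluded).**

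| Schedule | Labelled in 10.2.1 | Scheduled | Scheduled after first dose |
|---|---|---|---|
| Part A | 14 | 2 | 1 (V804) |
| 1.3.2.1 | 11 | 4 | 3 (V4 and V6 predose, V801) |
| 1.3.2.2 | 9 | 4 | 3 (V4, V6, V8, all predose) |

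V2 is the predose baseline in both Part B schedules. In Part A, post-dose chemistry draws number 14 - 2 = 12, because Day -1 and Day 1 predose come before dosing. Lipids are scheduled at 1 of those 12.

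**Step 3. Date V804.** The Study Day row is redacted. The amendment summary's HbA1c entry reads "Added line item for hemoglobin A1c to include time points at screening, Day - 1, Day" 29, then Day 85 and ED. In the HbA1c row, the first follow-up mark stands in the same column as the lipid mark, V804. The ocular row supports this: the days added were 15 and 43, and the note says "for follow-up Visit 802 and Visit 805, an ocular pressure assessment is required". That gives V802 = Day 15 and V805 = Day 43, with V804 at Day 29 between them. The gap from dose to first scheduled panel is 29 - 1 = 28 days.

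**Step 4. Check the volumes.** A Part A or B chemistry draw labelled with lipids (and without immunoglobulins) is 4.5 mL. A chemistry draw in the Part C 7-day group, labelled without lipids, is also 4.5 mL. The mismatch concerns which assays are run, not how much blood is taken. The Part A table total (501.5 mL) cannot be rebuilt because rows are redacted: the visible rows sum to 432 mL.

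**Step 5. Illustration only.** The human half-life is redacted. Assume mono-exponential decline with a half-life of 5, 10 or 20 days. The fraction of initial exposure left after d days is 2^(-d / half-life):

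- Day 15 (d = 14): 14%, 38%, 62%
- Day 29 (d = 28): 2%, 14%, 38%

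This shows how far the answer depends on an unknown. It ignores subcutaneous absorption, does not separate conjugate from free payload, and says nothing about when triglycerides would respond.

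**The case against.** The best case for the plan is that the blood-volume tables are a ceiling. Section 8 describes them as maximum numbers and volumes, Section 10.2.1 calls the counts approximate, and Section 8.2.5 gives precedence to the schedule. On that reading the extra labels are harmless, and sparse lipid sampling is a legitimate choice in a descriptive Phase 1 study. There are also safeguards. ED visits carry a panel, the investigator may add tests for immediate safety concerns, and Section 8 allows time points to change on emerging information. Part B dosing frequency is still open, so 1.3.2.2 may not be used for every cohort.

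Much of this stands. The schedule governs, and the labels are a reconciliation matter. But if the schedule governs, the sparse sampling is what will happen. The Part C 30-day table names lipids for particular days only, so the protocol does draw this distinction elsewhere. Unscheduled tests need a prompt, and a triglyceride rise may give no sign that would prompt one.

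A reader might infer that a comparison with prednisone would favour LY3872386. The documents do not support that. Section 4.2 says "only objective safety and PD biomarker results following prednisone or LY3872386 administration will be compared", but neither document names lipids in that comparison. SAP Section 10.6.15 plans no inferential safety analysis. The Part C Day 30 panel is itself predose, as are the on-treatment panels in 1.3.2.2, and the 7-day prednisone group has no lipid row.

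**Conclusion.** The point holds as a gap in measurement and an internal mismatch. For participants on schedule, Part A measures the named triglyceride risk at 1 of 12 post-dose chemistry draws, 28 days after the dose. Schedule 1.3.2.2 gives three on-treatment panels, all predose, and none between doses or after the last dose, whereas 1.3.2.1 has V801. Section 10.2.1 labels 14, 11 and 9 draws as including lipids, against 2, 4 and 4 scheduled.

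It does not follow that the trial would report no lipid effect. A sustained rise could show on Day 29 or at the predose panels, and the documents give no evidence on the time course of any triglyceride change. Nor is any blood volume shown to be wrong.

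The conclusion rests on column alignment for V804. It also assumes that the redacted study-day headers and comments hold no further lipid timing, which cannot be checked here. The improvement is worth making mainly because it costs little.

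**What to change.** Reconcile the schedules of activities with Section 10.2.1 so that both state the same lipid time points, and either align the two Part B schedules on post-treatment lipids or explain why they differ.

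While doing so, add the lipid panel to outpatient chemistry samples that already exist. Section 5.3.1 already requires a fast of about 10 hours before these visits:

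- **Part A:** V801 and/or V802, in addition to V804. The inpatient Day 7 sample is less suitable because that fasting rule covers outpatient visits only.
- **Schedule 1.3.2.2:** a between-dose chemistry visit (V3 and/or V7) and an existing follow-up chemistry visit, for example V803. V801 in that schedule has no chemistry draw.

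The cost is a small number of extra assays per participant. No visit or venipuncture is added, and on the tables' own labels the volume for these draws already allows for the panel. If the sponsor prefers the present sampling, the protocol should give the reason and the Section 10.2.1 labels should be corrected.
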